The primary endpoint of Phase I is safety, and the primary endpoint of Phase II is the degree of CD8+CD137+ T-cells infiltration in pre- and post-immunotherapy tumor specimens. Individuals will be censored at the date of last scan if no event has occurred. Secondary endpoints are OS, MFS, LPFS, surgical resectability, and pathologic response and as defined above. Exploratory endpoints include quality of life and immunologic, genetic/molecular and biomarker analysis, some of which will be correlated with clinical outcomes.

The Phase I portion is a 3+3 dose-escalation design to determine the maximum tolerated dose (MTD) or recommended phase 2 dose of BMS-813160 for use in the combination. It will evaluate two dose levels and enroll 3 to 12 patients depending on the number of dose limiting toxicities (DLT). All patients in Phase I portion will receive nivolumab, CCR2/CCR5 dual-antagonist (BMS-813160) and GVAX. DLT evaluation interval is the first cycle of treatment, beginning on the first day of treatment.

The MTD will be determined using the following escalation rules:

- A cohort of three patients will be entered at each dose level.
- If none of the subjects has a DLT during their first cycle, then the dose will be escalated and subjects will be enrolled at the next dose level.
- If 1 of 3 subjects at a given dose level has a DLT during the first cycle, then 3 additional subjects will be enrolled at the same dose level. Dose escalation will only occur if no additional DLTs are observed in the 3 additional subjects after they have been followed for one cycle of treatment.
- If 2 or more subjects at a dose level have a DLT during the first cycle, dose escalation will cease, and this dose level will have exceeded the MTD. New subjects will be enrolled at next lower dose level until that cohort has 6 subjects.
- A total of 6 patients must be enrolled at a dose level in order to declare MTD.
- The MTD will be defined as the dose of BMS-813160 in the combination in which < 2 of 6 patients experiences a DLT with the next higher dose having at least 2 of 3 or 2 of up to 6 patients experiencing a DLT.
- If ≤ 1 in 6 patients experience DLT at dose level 2, dose escalation will stop and this dose level will be the recommended dose for Phase II.

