4.11.2 Clinical Follow-up

All enrolled subjects who discontinue treatment without disease progression will enter the clinical follow-up portion of the trial. Subjects will begin the clinical follow-up period after they complete the EOT visit. Clinical follow-up visits will occur every 12 weeks (\pm 2 weeks) until: 1) start of a new antineoplastic therapy (information of the new cancer therapy will be collected), 2) disease progression, 3) death, 4) withdrawal of consent, or 5) study closure, whichever occurs first. Refer to **Section 9** for the schedule of assessments that should be performed at each visit. After disease progression or start of a new antineoplastic therapy, subjects will enter the survival follow-up portion of the trial (**Section 4.11.3**).

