4.11.3 Survival Follow-up

Subjects who discontinue treatment and have disease progression or start a new antineoplastic therapy will enter the survival follow-up portion of the trial. Subjects should be contacted every 12 weeks (\pm 2 weeks) to monitor overall survival. Information of other cancer therapies after discontinuation from the study treatment will be collected as well.

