10.1.4 **Overall Survival (OS)**

OS is defined as the duration of time from start of study treatment to time of death. Individuals will be censored at the date of the last scan if no event occurs.

10.1.5 **Local Progression-Free Survival (LPFS)**

LPFS is defined as the duration of time from start of treatment to time of first documented local progression or death, whichever occurs first. Individuals will be censored at the date of the last scan if no event occurs.

10.2 **Quality of Life**

Quality of life will be assessed using the European Organization for Research and Treatment in Cancer quality of life core cancer questionnaire with the pancreatic cancer module (EORTC QLQ-C30/PAN26, **Appendix D**). The EORTC QLQ-C30 is a multidimensional, 30-item questionnaire, which assesses five functional scales (physical, role, cognitive, emotional, and social), three symptom scales (fatigue, pain, and nausea/vomiting), a global health/QOL scale, as well as 6 single items.⁴³ The EORTC QLQ-PAN26 supplements the core questionnaire with 26 items specific for patients with pancreatic cancer.^{44, 45} These instruments have been validated in patients receiving treatment for metastatic and resected pancreatic cancer and are sensitive to identify treatment related changes in quality of life. We will offer subjects the option to complete their QoL questionnaires as an online REDCap survey within the 3 days prior to a visit or on paper the day of a visit. Patients who choose the online option will be sent a personalized link allowing their responses to be directly imported into our REDCap database. The REDCap database is HIPAA compliant and once survey responses are submitted, the link will no longer work and data will not be visible to the patients.

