12.6 Analysis of Secondary Endpoints – Efficacy Assessment

The secondary endpoints of interest are OS, MFS and LPFS, which are defined as the time from the study treatment initiation until death, evidence of metastatic disease or local

A Phase I/II trial of combination immunotherapy with nivolumab and a CCR2/CCR5 dual antagonist (BMS-813160) with or without GVAX following chemotherapy and radiotherapy for locally advanced pancreatic ductal adenocarcinomas (PDACs)

progression, respectively. The evaluable populations for OS, MFS and LPFS includes all subjects who receive at least one dose of study drugs (nivolumab, BMS-813160, or GVAX), and there will be a subgroup analysis for those who complete one cycle of study combination immunotherapy. If a patient is lost to follow-up, withdraws from the study or dies prior to being diagnosed with metastatic disease or local progression, or the study is ended prior to death, the patient will be considered censored at their last recorded follow-up. Kaplan-Meier survival curves will be constructed and the median survival estimates will be calculated with 95% confidence intervals using Greenwood's formula. Survival curves will be compared to historical data using log rank test. Because the study sample size is not powered for comparing the OS and MFS, comparisons with historical data will be performed for explorative purpose. Proportions of surgical resectability and pathologic response will be reported along with the corresponding binomial exact 95% confidence intervals.

Other secondary endpoints include surgical resectability and pathologic response. Surgical resectability will be determined by review of imaging and review of the subject's surgical candidacy (clinical status and tumor status) off trial after the patient completes off-trial chemotherapy and radiotherapy. Pathologic response will be graded after surgical resection or biopsy with comparisons of pre-and post-immunotherapy core biopsies or surgical samples. For each outcome, the proportion will be calculated with an exact 95% confidence interval. Individuals who drop out of the study due to treatment toxicity or other causes prior to outcome assessment will be counted as not resectable and non-responders. Logistic regression will be used to assess the impact of risk factors on each outcome. Time to event analyses will be used to assess the timing of resection and response.

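### The plan holds two incompatible censoring rules for overall survival, last scan and last recorded follow-up; if the last-scan rule is applied, OS is biased downward

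*Combined protocol and SAP*

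**What the plan says.** Three places set a censoring rule that can reach OS.

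- **Section 10.1.4** (OS definition): follow-up runs "to time of death. Individuals will be censored at the date of the last scan if no event occurs". The same last-scan sentence closes the MFS and LPFS definitions in 10.1.3 and 10.1.5.
- **Section 1.7** (study design): "Individuals will be censored at the date of last scan if no event has occurred". The sentence stands between the primary and the secondary endpoints. It names no endpoint and exempts none.
- **Section 12.6** (efficacy analysis): for OS, MFS and LPFS together, "the patient will be considered censored at their last recorded follow-up". That OS is included is clear from the condition "or the study is ended prior to death, the patient will be considered censored".

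Follow-up works as follows. Under 4.11.2, clinical follow-up visits, which include imaging, run until the first of several events, among them "1) start of a new antineoplastic therapy (information of the new cancer therapy will be collected), 2) disease progression, 3) death". Section 4.11.3 then states: "Subjects who discontinue treatment and have disease progression or start a new antineoplastic therapy will enter the survival follow-up portion of the trial". That portion consists of contact every 12 weeks, and the Survival FU column of the Section 9 schedules lists no CT or MRI. Sections 1.7 and 9 let patients with local progression continue study treatment, so their scheduled on-treatment scans continue too.

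Section 12.6 analyses OS by Kaplan-Meier with a median and 95% confidence interval, and by a log rank comparison with historical data. It calls that comparison exploratory because the sample is not powered for it.

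**The concern.** Censoring at the last scan suits MFS and LPFS, which are read on imaging. Death is not read on imaging, and the protocol sets up survival contacts in order to learn about it after scans have stopped.

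Under 10.1.4, what a contact adds depends on what it finds. A patient who progresses at month 6 and is reported dead at month 23 contributes 23 months and an event. A patient who progresses at month 6 and is reported alive at month 24 is censored at about month 6. Post-progression survivors leave the risk set early because they survived, and those who die stay in it. Kaplan-Meier and log rank both need censoring that is unrelated to prognosis, and this censoring is not.

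Two analysts working from the same protocol could therefore report different OS curves, each with a section to cite. The median and its interval will be reported whatever the power, and comparison with historical patients is a stated objective (1.2.2).

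**Working it through.** The plan gives no event count, power or expected median for OS, so there is no figure of its own to reproduce. The check has three steps.

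**1. Do the rules coincide?** They agree only if the last scan is also the last recorded follow-up. Once a patient is in survival follow-up, contacts are later than scans, so the rules differ for every such patient still alive.

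**2. Mechanism, by hand.** S(t) is the product of (1 − deaths/at risk) over the death times. Take ten invented patients: deaths at 6, 9, 12, 15 and 18 months, and five known alive at 24 months whose last scans were at 5, 8, 8, 11 and 24 months.

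- Last contact: S(12) = 9/10 × 8/9 × 7/8 = 0.700; S(18) = 0.700 × 6/7 × 5/6 = 0.500; median 18 months.
- Last scan: the numbers at risk at the death times become 9, 6, 4, 3 and 2. S(12) = 8/9 × 5/6 × 3/4 = 0.556; S(18) = 0.556 × 2/3 × 1/2 = 0.185; median 15 months.

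The deaths are the same in both; only the risk sets differ. The example shows direction, not likely size.

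**3. Size, by simulation** (400,000 patients per scenario).

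- From the documents: median MFS 7.7 months (historical SBRT study, Section 2.2) and 12-week intervals.
- Assumed, not in the documents: exponential times; 10% of MFS events are deaths; median post-progression survival 6, 8 or 12 months; uniform entry over 24 months; minimum follow-up 6, 12 or 24 months; 12-weekly scans ending at the metastasis event; last contact up to 12 weeks before cutoff.

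| Post-progression median (mo) | Minimum follow-up (mo) | True median OS | Last contact | Last scan | Shortfall, last scan | 12-month OS, true → last scan | 18-month OS, true → last scan |
|---|---|---|---|---|---|---|---|
| 6 | 6 | 15.7 | 15.7 | 14.2 | 1.5 | 62.4% → 58.9% | 42.9% → 36.1% |
| 6 | 12 | 15.6 | 15.6 | 14.6 | 1.0 | 62.3% → 60.0% | 42.8% → 37.8% |
| 6 | 24 | 15.6 | 15.6 | 15.3 | 0.3 | 62.4% → 61.8% | 43.0% → 41.5% |
| 8 | 6 | 17.8 | 17.9 | 15.4 | 2.4 | 67.6% → 63.4% | 49.5% → 40.4% |
| 8 | 12 | 17.8 | 17.9 | 15.9 | 1.9 | 67.7% → 64.6% | 49.5% → 42.7% |
| 8 | 24 | 17.8 | 17.8 | 17.0 | 0.8 | 67.5% → 66.6% | 49.5% → 46.8% |
| 12 | 6 | 21.8 | 22.0 | 17.2 | 4.6 | 74.2% → 69.0% | 58.9% → 46.8% |
| 12 | 12 | 21.8 | 21.9 | 17.8 | 4.0 | 74.2% → 70.2% | 58.8% → 49.2% |
| 12 | 24 | 21.8 | 21.8 | 19.4 | 2.4 | 74.2% → 72.4% | 58.8% → 54.1% |

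The last-scan rule discards on average 2.9 to 14.7 months of known-alive time per surviving patient. Last-contact censoring stays within 0.2 months of the true median and 0.4 points of true survival.

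A second set of assumptions (median time to progression 8 months, median post-progression survival 6 or 10 months) agrees. With 12–36 months of follow-up, the median falls from 16.9 to about 15.6 and from 21.7 to about 18.2 months. With 24–48 months it falls to 16.6 and 20.0.

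**The case against.** The strongest reply is that 12.6 is the statistical section, names OS and covers patients alive at study end. Survival contacts are naturally read as recorded follow-up, and under that rule the bias does not arise. The last-scan sentence in 10.1.4 matches its MFS and LPFS neighbours and may simply have been carried over, and the sentence in 1.7 names no endpoint. This stands as a reason to call the point a contradiction. It does not remove the point: 10.1.4 is the endpoint definition, it applies last-scan censoring to OS expressly, and no section is given precedence.

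A second reply is that scans do not stop at every progression. That also stands: patients with local progression can keep their scheduled scans while on treatment. The protection ends with treatment, since 4.11.2 and 4.11.3 do not separate local from metastatic progression.

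A third reply is that the effect is small beside sampling error. In simulated groups of 10 (8-month post-progression case), mean 12-month OS was 0.637, 0.645 and 0.667 under last scan and 0.681, 0.676 and 0.677 under last contact, a gap of 1 to 4 points. The binomial standard error is √(0.68 × 0.32 / 10) = 0.15, or 15 points. This stands and limits severity. A wide interval still does not justify a rule that shifts the estimate in a known direction when the data to avoid it are already collected.

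Finally, no go/no-go decision rests on OS (12.2 sets its thresholds on immune response), and a downward bias does not flatter the regimen's own curve. Both are correct and bear on severity.

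**Conclusion.** The plan states two incompatible OS censoring rules and does not say which governs. If 10.1.4 is followed, OS is biased downward: across the nine scenarios by about 0.3 to 4.6 months in the median, 0.6 to 5 points at 12 months and 1.5 to 12 points at 18 months. The direction was the same throughout. The size depends on assumed post-progression survival and follow-up and, for given survival, shrinks as follow-up matures.

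Three stronger readings are tempting, and the documents do not support them.

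- A reader might infer that OS in this trial will be biased. That follows only if 10.1.4 prevails over 12.6.
- A reader might infer that the historical comparison is tilted against the regimen. That also depends on how the controls were censored, which the documents do not state.
- A reader might infer that the trial's main conclusion is at risk. The Phase II primary endpoint is immune response, and OS is secondary, unpowered and compared with historical data only for exploration.

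This should be fixed before analysis, but it is not critical to the trial's validity.

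**What to change.** State one OS rule in 10.1.4 and 12.6: a patient not known to have died is censored at the date last known alive, by any visit, scan, survival contact or record review, up to data cutoff. In 1.7, limit the last-scan sentence to MFS and LPFS and give the OS rule beside it. Keep last-scan censoring in 10.1.3 and 10.1.5, and make 12.6 agree for those two endpoints.

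Update survival status close to the cutoff. On a strict 12-week contact grid, a residual bias of about 0.3 to 0.7 months in the median remained, which is small beside the last-scan effect at immature follow-up.

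The same edit to 12.6 should remove wording that can be read as censoring patients who die before metastasis or local progression, because 1.5.1, 10.1.3 and 10.1.5 count death as an MFS and LPFS event.

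The cost is a few sentences. No new data are needed, since the 12-weekly contacts are already planned, and the change can be made before the OS analysis.

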11. DATA REPORTING / REGULATORY REQUIREMENTS

Adverse event guidelines and instructions for AE reporting can be found in **Section 6 (Adverse Events: List and Reporting Requirements)**.

11.1 Data Management

All information will be collected on study-specific Case Report Forms (CRFs) by study staff. These data will be reviewed for completeness and accuracy by the Principal Investigator.

11.2 Safety Meetings

Scheduled meetings will take place weekly and will include the protocol principal investigator, study coordinator(s), data manager(s), sub-investigators (as appropriate), collaborators (as appropriate), and biostatisticians (as appropriate) involved with the conduct of the protocol. During these meetings matters related to the following will be discussed: safety of protocol participants, validity and integrity of the data, enrollment rate relative to expectation, characteristics of participants, retention of participants, adherence to protocol (potential or real protocol violations), data completeness, and progress of data for objectives.

Monthly teleconferences will be scheduled to include the Investigator and BMS representatives. During these meetings, the Investigator shall provide BMS with study progress updates. The Investigator will provide a summary of key points from the weekly meetings with a focus on safety of the protocol participants, enrollment status, and progress of data for objectives. In addition, BMS will provide safety and applicable program updates to the IND Sponsor.

11.3 Monitoring

The SKCCC Compliance Monitoring Program will provide external monitoring for JHU-affiliated sites in accordance with SKCCC DSMP (Version 6.0, 02/21/2019). The SMC Subcommittee will determine the level of patient safety risk and level/frequency of monitoring. Data monitoring of this protocol will occur on a regular basis with the frequency dependent on the rate of subject accrual and the progress of the study. The protocol will be monitored internally by the Principal Investigator. The protocol will be monitored externally by the SKCCC CRO in accordance with SKCCC guidelines. Additional data and safety monitoring oversight will also be performed by the SKCCC Safety Monitoring Committee (SMC - as defined in the DSMP) and a Data and Safety Monitoring Board (DSMB) as detailed below.

Interim analysis of toxicity, outcome and ongoing scientific investigations will be performed at least annually by the Sidney Kimmel Comprehensive Cancer Center Data Safety Monitoring Board (SKCCC DSMB). The SKCCC DSMB will review aspects of this trial that are outlined in the responsibilities section of the Data and Safety Monitoring Board (DSMB) Guidance. If the committee decides that amendments should be made to this trial,

A Phase I/II trial of combination immunotherapy with nivolumab and a CCR2/CCR5 dual antagonist (BMS-813160) with or without GVAX following chemotherapy and radiotherapy for locally advanced pancreatic ductal adenocarcinomas (PDACs)

recommendations will be made in writing to the Study Principal Investigator. The study team will submit modifications to the IRB within 60 days of receipt from the DSMB. The Associate Director of Clinical Research, will arbitrate any disagreements between the DSMB and the study Principal Investigator. These changes may include early termination of accrual if deemed appropriate.

[name] will be holding the IND for this study. She will comply with all regulated reporting requirements to the FDA.

12. STATISTICAL CONSIDERATIONS

12.1 Study Design/Endpoints

This is a single center, open-label, phase I/II study to evaluate the activity of combination nivolumab and a CCR2/CCR5 dual antagonist (BMS-813160) with or without GVAX in patients with locally advanced pancreatic cancer (LAPC) in conjunction with FOLFIRINOX-based chemotherapy, radiation therapy, and possible surgical therapy.

The primary endpoints of Phase I are study-related adverse events according to National Cancer Institute Common Toxicity Criteria for Adverse Events (NCI CTCAE, Version 5.0) and incidence, nature and severity of all adverse events that occur on and after Cycle 1, Day 1 immunotherapy.

The primary endpoint of Phase II is the proportion of patients treated with nivolumab and a CCR2/CCR5 dual antagonist (BMS-813160) with or without GVAX who achieve immune response, defined as >80% increase of infiltration of CD8+CD137+ T-cell density after the treatment compared to baseline before treatment.

The secondary endpoints are study-related adverse events (for Phase II), overall survival (OS), metastasis free survival (MFS), local progression free survival (LPFS), surgical resectability rate, and pathologic response rate.

Exploratory endpoints include:

- Quality of life
- Evaluate changes in CD4+OX40+ and CD8+OX40+ cell density in pre- and post-treatment specimens via Halo-analysis.
- Evaluate changes in the expression of CCR2, CCR5, CXCR4 and PD-L1/PD-1 pathways in pre- and post-treatment specimens by nanostring analysis.
- Evaluate changes in M1 vs. M2 TAM, Teff:Treg, and MDSC by multiplex IHC.
- Evaluate, through genomic sequencing and RNA sequencing, mutated neoepitope specific T cell repertoire by TCR clonality and/or the MANAFEST assay in pre- and post-treatment tumor specimens and in peripheral blood lymphocytes over time on treatment.
- Cytokine/chemokine assays to assess changes in intratumoral inflammatory markers

A Phase I/II trial of combination immunotherapy with nivolumab and a CCR2/CCR5 dual antagonist (BMS-813160) with or without GVAX following chemotherapy and radiotherapy for locally advanced pancreatic ductal adenocarcinomas (PDACs)

- Peripheral antigen specific T-cell responses
- Intratumoral antigen specific T-cell responses
- Biomarker marker changes (including standard protein biomarkers such as CA 19-9) and correlation to evaluate for prognostic or predictive factors
- To assess correlation between immune parameters and clinical outcomes using univariate and multivariate Cox regression models

12.2 Sample Size/Accrual Rate

Each year, approximately 250 patients with newly diagnosed locally advanced pancreatic cancer are seen at JHH. Approximately, 50% of these patients will potentially be enrolled in clinical trials.

Phase I: 3-12 patients (3+3 design with Nivo+GVAX+BMS-813160 at two dose levels, primary endpoint - safety).

Phase II: up to 15 patients (primary endpoint - immunologic)

The first 10 patients will be randomized 1:1 into two arms:

Arm A: *nivolumab*+ *BMS-813160*

Arm B: *nivolumab*+ *BMS-813160*+ *GVAX*

Up to 5 additional patients will be assigned to Arm C: *nivolumab* + *BMS-813160* in Cycle 1

Due to the availability of BMS-813160, the enrollment of Phase II Arm A and Arm B will close early before full accrual under the original protocol. An amendment is required to change the design of the phase II portion. The analysis plan is also changed accordingly. The primary endpoint remains to be immunologic response, defined in Section 12.1 above.

The analysis will be performed separately in two groups of patients receiving either *nivolumab*+ *BMS-813160* (Group 1), or *nivolumab*+ *BMS-813160*+ *GVAX* (Group 2). Group 2 will include patients treated with the triplet regimen at the RP2D during both Phase II and Phase I portion. We expect up to 10 patients in Group 2 (including 6 treated at the 300mg dose in Phase I and 5 patients in Arm B of Phase II). A rate of immune response of 5% or lower is not considered worthy of further investigation, whereas immune response rate of at least 30% is consider worthy of further study.

Group 1 will have 8, up to 10, patients treated with the doublet regimen during Phase II (including up to 5 patients in Arm A and 3 to 5 patients anticipated to be enrolled to Arm C who receive *nivolumab* + *BMS-813160* in Cycle 1 and *nivolumab* + *GVAX* from Cycle 2 and after). It allows us to make preliminary assessment of immune response.

The probability of events under different true immune response rate is as follow:

number of responders out of 8 patients	True response rate				
	0.3	0.25	0.2	0.1	0.05
>=1	0.943	0.900	0.832	0.570	0.337
>=2	0.745	0.633	0.497	0.187	0.057
>=3	0.448	0.321	0.203	0.038	0.006
number of responders out of 10 patients					
	0.3	0.25	0.2	0.1	0.05
>=1	0.972	0.944	0.893	0.651	0.401
>=2	0.851	0.756	0.624	0.264	0.086
>=3	0.617	0.474	0.322	0.070	0.012

